The total number of participants that will be enrolled into the 6-month feasibility trial is 70. It is estimated that we will screen ~1,700 participants to achieve this recruitment goal. Since the initial contact is via an online link, there will be many incomplete responses driving up the number of screened-out participants.

How was sample size determined?

We based the sample size of 70 for this pilot feasibility trial on necessities for examining feasibility. This sample size allows us to recruit online groups of 35 which we have demonstrated in an ongoing study is feasible and breeds regular engagement. Our previous work with smaller online groups (i.e., n=12)^{33,34} showed that presence of a few quiet participants can result in a fairly rapid decline engagement among entire group.^{33,34} We plan on enrolling waves of 70 participants (35 participants in each treatment condition), thus the feasibility trial allows to pilot recruitment procedures and assess feasibility of recruitment and engagement in the Facebook groups.

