Retention: With n=35 per treatment condition, the 95% confidence interval (CI) for the estimated retention rate in each condition will be within $\pm 11.8\%$ if the observed retention is 85%. Thus, given n=35 per condition, the lower limit of the 95% CI for the observed retention rate in either treatment condition should not be lower than 73.2%. App use: With n=35 per treatment condition, the lower limit of the 95% CI for observed proportion of 80% of participants meeting targets for app use in either treatment condition should not be lower than 66.7%. Acceptability: Assuming 85% retention, with n=30 available per treatment condition, the lower limit of the 95% CI for observed proportion of 80% of participants providing high acceptability ratings in either treatment condition should not be lower than 65.7%. Exploratory outcomes: We propose 6-month change in weight, 6-month change in weight loss problem solving, counselor time, and group cohesion at 6 months as exploratory because a true test of efficacy will require a fully powered trial informed by the refined procedures that will result from this feasibility study. Since the primary focus of this pilot trial is to assess feasibility to inform the design of the subsequent efficacy trial and the trial was powered to assess feasibility, not demonstrate efficacy, we only have 80% power to detect differences far larger than we expect to find in the subsequent efficacy trial. For example, taking an intent-to-treat approach, we have 80% power to detect differences of ≥ 0.68 SDs in weight change and the other exploratory outcomes. For example, if the SD=6.0%^{10,11} weight loss, we only have 80% power to detect differences in percent weight loss $\geq 4.1\%$, a difference 1.5-4 times larger than observed in previous research.

How are participants recruited?

Participants will be notified or approached about this research study through digital ads on various platforms (e.g., search engines, health websites, and social media platforms). One method we may use will be in collaboration with a company called Build Clinical. Build Clinical is a technology company that enables academic researchers to engage the exact populations needed for a given study.³⁸ Build Clinical will create the advertisements and landing page as well place the digital ads on the various platforms across the Internet. Participants will learn about the research study through these digital ads that will appear

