Adverse Events. Adverse events will be documented during the intervention and follow-up phase. AE's will be formally assessed at follow-ups by asking questions in the REDCap survey. During the intervention, AE's will be documented when a participant reports it to the weight loss counselor or posts it in the Facebook group. If it is reported during the intervention, the counselors will notify a research coordinator within 24 hours of learning of the event. UConn will then report it to the IRB (immediately if it's serious, or at the time of annual renewal). If participants gain 5% or more weight during the intervention, this will be treated as an adverse event. The participant will receive a phone call from a research coordinator, and they will be asked questions to figure out the cause of their weight gain. We will also assess Binge Eating Disorder (BED) at this time. If BED is present, we will treat it as a study-related AE. We will only assess BED once, even if there are multiple AEs for weight gain. Participants will not be removed from the intervention if they have 5% or more weight gain.

After we have completed all data analysis for the study, and it is put into a master dataset we will delete the Facebook group.

Measures

Data Collected	List of Measures	Screening/ Baseline	6-month pilot	F/up	Method
Inclusion/Exclusion criteria	Initial screening survey*	X			REDCap or Qualtrics
BMI	Height	X			REDCap
	Weight	X	X	X	REDCap
Demographics	Marital status, education, race/ethnicity, sexual orientation, work status, household income, household members*	X			REDCap
Binge Eating Disorder	SCID Eating Disorder Examination Questionnaire ⁴⁷		X**	X**	REDCap
Depression	Patient Health Questionnaire (PHQ-8 ⁴⁸)	X			REDCap
Weight Loss Problem Solving Skills	Social Problem-Solving Inventory-Revised (Modified for weight loss) ⁴⁹	X		X	REDCap
Group Climate Questionnaire	Group cohesion ⁵¹⁻⁵⁶			X	REDCap

Engagement	Facebook Engagement	X		Grytics into REDCap
App use	App use data*	X		WPI server and REDCap
Diet tracking	Data extraction*	X		MFP records
Usability Feedback	Acceptability, contamination, satisfaction, burden*, and user engagement ⁵⁰		X	REDCap and focus group

* = investigator derived

** = as needed for AEs

Psychometric properties for non-investigator derived measures:

SCID Interview for BED: The SCID's severity scales demonstrated substantial internal consistency (all Cronbach's alphas >.80), test-retest reliability, concurrent, and predictive validity.⁴⁷

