App use. In the Habit app condition, descriptive statistics will be performed to summarize the number of days participants used each feature. These numbers will be inspected relative to the use targets defined for each feature. In the MyFitnessPal condition, descriptive statistics will be performed to summarize the mean number of days participants used MyFitnessPal over the 6-month intervention. A total “app compliance” score will be developed for each participant based on the percent of days they completed of their assigned use. Exploratory analyses using ANOVAs will compare conditions on app compliance scores at 6 months.

Retention. We will calculate retention as the proportion of participants who complete the 6-month follow-up assessment in each condition and report this information using a CONSORT diagram.

Engagement. Number of Facebook reactions (e.g., like, care, wow, etc.), replies, posts, and polls per participant during the 6-month program.

Acceptability. We will report participant satisfaction.

Burden. Using descriptive statistics, we will summarize burden scores in both treatment conditions. ANOVAs will be used to compare conditions on burden.

Group Cohesion. Using ANOVAs, we will compare conditions on group cohesion and climate total and subscale scores at 6 months.

Contamination. We will report the percent of participants that used any outside programs that provided weight loss coaching/problem solving.

Weight Change (exploratory). We will calculate weight changes from baseline to 6 months in each treatment condition. We will compare percent weight change from baseline to 6 months across the two treatment conditions using a mixed effects model approach with weight as the continuous outcome variable, and time as a covariate using percent weight change calculated from all available objectively measured weekly weights. To adjust for within-subject correlation in the mixed model, first we will estimate an unstructured within-subject covariance matrix; estimates may suggest that a simpler structure, e.g., compound symmetry (random intercept) is satisfactory.

Changes in weight loss problem solving. Using a mixed effects model with weight loss problem solving as the continuous outcome variable, we will compare conditions in change in weight loss problem solving from baseline to 6 months.

Group cohesion. Using ANOVA, we will compare conditions on group cohesion measures at 6 months.

Study Removal

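### The problem-solving comparison does not say how the baseline score is used; the usual reading is a change-score analysis, less precise than a baseline-adjusted one (minor)

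*Combined protocol and SAP*

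**What the plan says.** The Analytic Plan gives problem solving one sentence, under Changes in weight loss problem solving. The model is introduced as "Using a mixed effects model with weight loss problem solving as the continuous outcome variable", and the comparison as "we will compare conditions in change in weight loss problem solving from baseline to 6 months". Nothing more is specified. The text does not list fixed effects, does not say whether the baseline score is an outcome or a covariate, and does not say whether the two conditions share a baseline mean.

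The Measures table lists the instrument as "Social Problem-Solving Inventory-Revised (Modified for weight loss" and marks it at Screening/Baseline and at F/up, with no measurement in between. The baseline score is therefore in hand for everyone who completes on-boarding, and the analysis has two time points.

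The sample size section sets the status of the outcome: "We propose 6-month change in weight, 6-month change in weight loss problem solving, counselor time, and group cohesion at 6 months as exploratory". It also gives one figure for this group of outcomes: "we have 80% power to detect differences of ≥ 0.68 SDs in weight change and the other exploratory outcomes".

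**The concern.** Putting the baseline score into a mixed model as a repeated outcome is not the same as adjusting for it. With two time points and a separate baseline mean for each condition, the condition-by-time term is the difference in mean change. That contrast subtracts the whole baseline score, whereas regression on baseline subtracts only the predictable part. When rho is below 1, the change score carries extra noise, and a chance baseline difference between two small arms moves the estimate.

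The stake is the precision of one exploratory contrast, on a skill that the Habit app is built to support, in a pilot meant to inform a later efficacy trial. There is also a small question of analyst choice: the two standard forms of the model can give different estimates on the same data, and the text does not settle which one is meant.

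**Working it through.** **Inputs.** There are 35 per condition (sample size section: "35 participants in each treatment condition"). About 30 per condition have follow-up (same section: "Assuming 85% retention, with n=30 available per treatment condition"; 0.85 × 35 = 29.75). Power is 80%. Three inputs are assumptions because the documents do not give them: two-sided alpha of 0.05 (in line with the 95% CIs used elsewhere), equal score variance at the two times, and rho between 0.3 and 0.8. The reported Cronbach's alpha of 0.95 is internal consistency and does not supply rho.

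**Step 1: reproduce the plan's figure.** For a two-sample comparison with n = 35 per arm, the normal approximation is (1.960 + 0.842) × √(2/35) = 2.802 × 0.239 = 0.670 SD. The noncentral t gives 0.679 SD, and power 0.801 at 0.68 SD. The stated 0.68 SD reproduces, with no gain from baseline built in. At n = 30 per arm the t-based figure is 0.736 SD.

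**Step 2: variance of the two contrasts.** With score variance set to 1, the per-person variance is:

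- change score: 1 + 1 − 2rho = 2(1 − rho)
- baseline-adjusted: 1 − rho²
- ratio: (1 − rho²) / [2(1 − rho)] = (1 + rho)/2, below 1 whenever rho is below 1.

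**Step 3: effect of a chance baseline difference d.** Given d, the expected carry-over at 6 months is rho × d. The change contrast is therefore shifted by rho × d − d = −(1 − rho)d.

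**Step 4: numbers.** Detectable differences are in SDs of the score at 30 per arm, from 0.736 × √(variance).

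| rho | Change variance | Adjusted variance | Ratio | Variance cut | SE cut | Detectable, change | Detectable, adjusted | Shift from d |
|---|---|---|---|---|---|---|---|---|
| 0.3 | 1.40 | 0.91 | 0.65 | 35% | 19% | 0.87 | 0.70 | −0.7d |
| 0.5 | 1.00 | 0.75 | 0.75 | 25% | 13% | 0.74 | 0.64 | −0.5d |
| 0.7 | 0.60 | 0.51 | 0.85 | 15% | 8% | 0.57 | 0.53 | −0.3d |
| 0.8 | 0.40 | 0.36 | 0.90 | 10% | 5% | 0.47 | 0.44 | −0.2d |

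For scale, the standard error of the baseline difference at 35 per arm is √(2/35) = 0.24 SD. An imbalance of that size at rho = 0.5 shifts the change contrast by 0.5 × 0.24 = 0.12 SD.

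**Step 5: which mixed model is which.** Four analyses were fitted to one simulated complete data set (35 per arm, rho = 0.5):

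- mixed model with condition, time and their interaction: estimate −0.1588, SE 0.2306
- change-score regression: estimate −0.1588, SE 0.2306
- ANCOVA: estimate −0.068, SE 0.198
- mixed model with a common baseline mean: estimate −0.070, SE 0.199.

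Over 2,000 simulated trials per value of rho, ANCOVA and the common-baseline model had the same variance. It was 0.68, 0.74 and 0.88 of the change-score variance at rho = 0.3, 0.5 and 0.7, against 0.65, 0.75 and 0.85 in theory.

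**The case against.** The strongest reply is that the plan never says the analysis is unadjusted. It names a mixed model and stops. One standard form of that model, with a common baseline mean, already has the precision of ANCOVA, as step 5 shows. This stands: the documents show an unspecified model, and a deliberate choice to ignore baseline cannot be read from them. It does not remove the point, because free baseline means are the usual form and nothing written rules them out.

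The second reply is that the consequence is small. The outcome is exploratory, the sample size section says openly that only differences far larger than expected are detectable, and moving from 0.74 to 0.64 SD does not change that. This also stands and sets the severity.

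Some stronger readings are tempting, and the documents do not support them:

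- *The 0.68 SD figure shows that an unadjusted analysis was intended.* It is one blanket figure for "SDs in weight change and the other exploratory outcomes". Those outcomes include group cohesion, which has no baseline measurement, so the figure is compatible with either model. It is also arithmetically correct.
- *Chance imbalance passes in full into the change estimate.* The shift is −(1 − rho)d, which is half of d at rho = 0.5, and the contrast is unbiased over randomizations.
- *The percent weight change model has the same fault.* That outcome is already scaled to baseline weight and uses weekly weights, so the two-time-point formula does not carry over. No calculation here supports a gain there.

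**Conclusion.** The point holds as a minor one. The problem-solving model is under-specified on baseline, and its usual reading gives away precision that costs nothing to keep. Over assumed correlations of 0.3 to 0.8 the loss is 35% down to 10% of the variance. The example of 0.74 against 0.64 SD holds at rho = 0.5 with 30 completers per arm and two-sided 0.05. If a common baseline mean was meant, the loss is essentially nil.

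The result rests on equal variances at the two times and on complete data. With dropouts, the match between the interaction model and the change score is only approximate. The variance formulas also ignore the small cost of estimating the baseline slope, which the simulations include.

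A reader might infer that the sample size or a feasibility conclusion is affected. Neither is: problem solving is not among the feasibility outcomes listed in the Aims, and no target depends on this contrast.

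**What to change.** Replace the problem-solving sentence in the Analytic Plan with one that fixes the model. Either of these will do:

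- the 6-month score is modelled with condition and baseline score as covariates (ANCOVA); or
- baseline and 6-month scores are modelled jointly in a mixed model with terms for time and for condition at 6 months, and with both conditions constrained to a common baseline mean.

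In either case, report the adjusted difference between conditions at 6 months with its 95% CI. If the second form was intended all along, saying so closes the point.

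The cost is one sentence, settled before the follow-up scores are examined. No new data, visits or participants are needed, and the stated 0.68 SD can stay as it is.

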Study Design: Participation starts with a simple information sheet, online eligibility survey, orientation webinar, e-consent, and then another survey to collect baseline assessment data. Eligible participants will then complete an on-boarding process, which includes app and scale set up. Participants will then be randomized and complete a 6-month intervention, and a 6-month follow-up assessment after the intervention ends (survey, focus group, and weigh-in).

Recruitment: We will post online recruitment ads that will contain a link to a simple information sheet and an online survey containing the screening questions. Ads that are done with Build Clinical will lead the participant to a landing page that will give them some more information about the study and then will have the link to bring them to the simple information sheet and survey. See recruitment section (starting on page 8) for full recruitment details.

Screening

Inclusion Criteria

- 18-65 years old
- BMI 27-45 kg/m²
- Wi-Fi connectivity at home
- Logs into Facebook at least 5 days per week over the past 2 weeks
- Has posted/replied on Facebook at least once a week in the past 2 weeks

- Able to participate in the study in English
- Interested in losing weight

Age justification: Children under 18 require different programming for weight loss and maintenance given their developmental needs. Weight loss is for elderly adults should be medically supervised, something this study is not offering.

Exclusion Criteria

- Under the age of 18 and over the age of 65
- BMI under 27 or over 45 at screening; then under 27 at the point of the first weight on scale
- Does not have Wi-Fi connectivity at home
- Does not have a Facebook account
- Does not log into Facebook at least 5 days per week over the past 2 weeks
- Did not post/reply on Facebook once a week over the past 2 weeks
- Not able to participate in the study in English
- Does not live in the United States
- Not interested in losing weight
- Pregnant/lactating or plans to become pregnant during study period
- Reports having bipolar disorder, substance abuse, psychosis, an eating disorder, or severe depression
- Had bariatric surgery or plans to have surgery during the study
- Currently taking medication affecting weight
- Has lost $\geq 5\%$ of weight in past 3 months
- Is participating or intends to participate in another weight loss program during the study that provides coaching or problem solving

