- Chronic pain that interferes with the ability to exercise

- Type 1 Diabetes
- Type 2 Diabetes
- Unable to make dietary changes or increase physical activity
- Unable to walk ¼ mile unaided without stopping
- Currently smokes or vapes nicotine
- No phone connectivity at home and work
- Has a digestive disorder/condition that precludes dietary changes
- Meets criteria for severe depression on the PHQ-8 (score of >19)
- Does not currently own a smartphone
- Smartphone type and/or version not meeting app requirements
- Participated in previous weight loss studies under the PI
- Unable to attend the orientation webinar
- If UConn employee/student, has concerns about being in a Facebook group with other UConn faculty, staff, and students
- Had major surgery in past 6 months and have not been cleared by their doctor to resume physical activity and diet changes
- Plans to have major surgery in the next 6-months
- Has an implanted cardiac defibrillator or pacemaker
- Did not complete screening and on-board processes of study (screening survey, webinar, e-consent, baseline survey, app set-up, scale set-up, etc.)
- Not willing to be audiotaped for focus groups
- Prisoner; or
- Unable to provide consent

Participants will complete screening procedures online since they may be located anywhere in the country. The screening survey will first have a description of the study and the data we will collect from them at that point (the simple information sheet). At the bottom of the information sheet, they can mark that they are interested in participating or not interested. If they mark that they are interested, it will bring them to the screening

questions to determine eligibility. The survey logic within REDCap will determine eligibility for participation based on participant responses. BuildClinical also had logic to determine eligibility. If they are ineligible, they will be notified after the survey is submitted. If they are eligible to proceed, they will be contacted by the study team via email to book a time to attend a live informational webinar.

We will not require PCP approval since we assess exclusionary medical conditions during the screening process. If conditions are reported that might put the participant at risk during the intervention, they will be excluded.

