After the baseline survey is completed, for those that are still eligible, UConn will ship a study scale to the participant. Once the participants receive their scale, UConn staff will give the participant an option to set it up themselves or schedule a call to help them set up the scale and ensure that it is working, and we can access their data. UConn staff will then collect a baseline weight from participants to confirm their BMI for eligibility reasons.

After the BMI has been confirmed, UConn staff will do a final eligibility check, going through all previous steps done by the participant and double-check to confirm that they are eligible. If they are not, UConn staff will notify them via email. If they are eligible, UConn staff will engage in a series of emails with the participants to help them set-up the study apps and confirm they are working. If the participant prefers, the set-ups can be done over the phone as well.

Participants will need to complete both surveys (screening and baseline), webinar, consent, set-up the scale and provide the study team with a baseline weight to confirm BMI (done with scale we ship to them), and set-up all study apps before being randomized into the trial. Participants will be randomized into one of two groups.

Ineligible participants will be notified either automatically or by the research assistant/coordinator via email that they do not meet criteria for the study. Staff will use a generic response about how their pattern of responses is not a match to our eligibility criteria (the examples are provided in additional documentation). If they want to know specifics as to why they were ineligible, staff will refer the participant to email the PI so they can have a more detailed discussion about eligibility. This is being done to avoid upsetting participants and letting [name], a clinical psychologist, handle communication of more sensitive information.

Intervention

Participants will be randomized into the Habit app or calorie tracking app program. Both programs are 6-month online weight loss interventions and involve these major components: 1) monthly group meetings, and 2) counselor-led Diabetes Prevention Program (DPP) lifestyle intervention delivered via private Facebook group. The Habit condition use the Habit app and the calorie tracking condition will use a commercial app for calorie tracking.

1. Monthly Group Meetings

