During the 6-months of the intervention, the program will have monthly breakout sessions for participants to join via WebEx or within Facebook “rooms.” Each month, the counselor and/or study staff will schedule a 45-minute event within the Facebook group that will allow participants to RSVP to, if they so wish. When they click on the event on the day/time it was scheduled for, they will be brought to the events tab in the Facebook group where they can click on the WebEx link and/or internal Facebook link to bring them to the breakout session. The counselor and/or staff member will be leading the sessions. Each month will be based on a topic around achieving a healthy lifestyle (or barriers to achieving a healthy lifestyle). The participants will have the option pick the topic for each week if they’d like. If not, the study team will pick a topic. The counselor will talk about the topic of the month and will promote discussion between participants. As needed, the counselor will pose discussion questions related to the topic of the week to help facilitate the discussion. The meetings will be recorded and posted in the Facebook group for those who missed. If they do not wish to be recorded, they will be able to leave the meeting and watch the video after it is posted in the group or turn their video off. The point of these breakout sessions is for group members to connect on a topic, do some brainstorming, and get to know each other better.

2. Facebook Group

Participants will be asked to join a private Facebook group where they will receive weight loss counseling based on the Diabetes Prevention Lifestyle Intervention (DPP). The Habit and calorie tracking app conditions will each have their own Facebook group. The group leader will counsel participants toward achieving and maintaining the exercise and diet goals to lose weight. The participants will also be asked to participate in the Facebook group by reading and engaging with the posts from the counselors. Additionally, they will be asked to engage with their fellow participants through comments, reactions, and posts. The participants will be able to privately message their counselor if they do not want to share something with the group. A detailed description of the how the Facebook group will operate is below.

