Follow-ups. Follow-ups are completed after the intervention ends. Participants will receive a link to an online REDCap follow-up survey in the beginning of the week following the end of the intervention. This survey will be a repeat of some of the measures assessed at baseline (indicated in the measures table below) and questions to solicit participants' feedback on the program and app. The participants will also weigh-in one final time after the intervention ends. Finally, the participants will schedule and attend a focus group call lead by study staff to get their feedback on their experience in the intervention.

Focus groups. A focus group will occur in a WebEx setting starting the week after the end of the intervention. The focus group will last for approximately 30-60 minutes (depending on how many participants are in attendance) and will include a discussion about likes and dislikes of the intervention as well as their opinion on various features of the app and intervention. All focus groups will be conducted via WebEx including 1-4 participants on each call. Any participants who are unable to attend the focus group will receive the focus group questions through an e-mailed survey. We will e-mail the survey twice. At the time of the 2nd e-mail, we will also text them to let them know to check their e-mails. If there is no response from the participant after the 2nd e-mail, we will make no further attempts to contact them. The focus groups will be recorded on WebEx and then will be transcribed using Otter.ai, a web-based transcription software.

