Participants will be removed from the study if: 1) they do not complete all screening, baseline, and on-boarding procedures (two surveys, consent, webinar orientation, app set-up, and scale set-up, join the Facebook group), 2) become pregnant during the study period, 3) post inappropriate content in the Facebook group (e.g., bullying/harassment of others, hate speech, violent/graphic content, violating privacy of others etc.), and 4) if they choose to withdraw their participation from the study. Participants reporting that they would like to withdraw from the study will be given the option to 1) withdraw from all intervention-related activity and contacts, but still complete the final assessment or 2) withdraw from the study completely with no additional study contact. If a participant becomes pregnant during the study, they will be withdrawn from the intervention, but will be asked to complete the follow-up assessments.

Potential risks

Potential risks for being in this study includes injury while exercising, accidental exposure of personal information, and discomfort with study procedures (e.g., feeling uncomfortable

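### The rule removing people who do not join the Facebook group appears to reach randomized participants, and no 6-month assessment is stated for them

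*Combined protocol and SAP*

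**What the plan says.** **Removal.** Study Removal gives four grounds for removal from the study. The first is failure to complete the screening, baseline and "on-boarding procedures (two surveys, consent, webinar orientation, app set-up, and scale set-up, join the Facebook group" steps. The others are pregnancy, inappropriate content in the group, and the participant's own choice.

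**Order of steps.** Methods, Study Design: "Eligible participants will then complete an on-boarding process, which includes app and scale set up. Participants will then be randomized". The Baseline section lists the two surveys, webinar, consent, scale and baseline weight, and requires participants to "set-up all study apps before being randomized into the trial". The matching item in Exclusion Criteria reads "Did not complete screening and on-board processes of study (screening survey, webinar, e-consent, baseline survey, app set-up, scale set-up, etc". None of these names the Facebook group, although the last list is open-ended. Under Intervention, Facebook Group: "The Habit and calorie tracking app conditions will each have their own Facebook group".

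**Follow-up.** The Follow-ups section says: "Participants will receive a link to an online REDCap follow-up survey in the beginning of the week following the end of the intervention". It does not say whether a person already removed from the study counts as a participant for this purpose.

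**Analysis.** The Analytic Plan specifies intent to treat and defines retention, by condition, as the proportion completing the 6-month assessment. The sample-size section gives the precision for retention: "With n=35 per treatment condition, the 95% confidence interval (CI) for the estimated retention rate in each condition". Acceptability alone is planned on a reduced number, "with n=30 available per treatment condition".

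**The concern.** A rule that excludes people for incomplete set-up does no harm to a randomized comparison if it acts before allocation. It is different if it acts after allocation, because it then removes people from a randomized arm for something they did or did not do once assigned.

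Retention is one of the feasibility outcomes named in the Aims. If someone is removed by rule and not assessed, they count as not retained even if they would have completed follow-up. Part of the reported loss would then come from the rule and not from participants. Their 6-month problem-solving score and final weight would also be lost. Imputation can stand in for a missing weight or score, but it cannot restore a completed follow-up to the retention count.

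**Working it through.** **1. When does joining happen?** On-boarding precedes randomization in Study Design, and the explicit pre-randomization list in Baseline omits the group. Joining is described under Intervention, which opens with randomization, and there is one group per condition. A person cannot be directed to the group for their condition until the condition is known. Joining therefore appears to follow allocation, and the first removal ground appears to reach randomized participants.

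**2. What follow-up is stated for each ground?**

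| Ground in Study Removal | 6-month assessment stated |
|---|---|
| 1. Incomplete on-boarding, including not joining | None stated |
| 2. Pregnancy | Asked to complete it |
| 3. Inappropriate content | None stated |
| 4. Own choice to withdraw | Offered the final assessment |

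The participant-retention paragraph in Data Safety Monitoring and the Privacy and Confidentiality section deal only with people who choose to drop out or withdraw. The gap is the randomized person removed under ground 1 or 3 who has not asked to leave.

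**3. The plan's own precision figures.** Wald 95% lower limit = p − 1.96 × √(p(1 − p)/n).

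- Retention, p = 0.85, n = 35: half-width 11.8%, lower limit 73.2%. Matches the plan.
- App use, p = 0.80, n = 35: lower limit 66.7%. Matches.
- Acceptability, p = 0.80, n = 30: lower limit 65.7%. Matches.

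Retention and app use were therefore planned on the full arm of 35.

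**4. Effect of a removal on retention, denominator fixed at 35.** One person is 1/35 = 2.9 points. The documents give no number of non-joiners or removals, so the counts here are assumptions. Suppose one removed person in an arm would have completed follow-up:

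- 31/35 = 88.6% (lower limit 78.0%) is reported as 30/35 = 85.7% (74.1%); or
- 30/35 = 85.7% (74.1%) is reported as 29/35 = 82.9% (70.4%).

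A removed person who would not have completed anyway changes nothing. For 1, 2 or 3 assumed removals in an arm, the fall is therefore 0 to 2.9, 0 to 5.7 or 0 to 8.6 points.

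**5. If removed people were left out of the denominator.** With 30 completers and two removed, 30/35 = 85.7% would become 30/33 = 90.9%. The plan does not say this will be done. The figure shows only why the denominator should be written down.

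**The case against.** **Timing is inferred.** The two main apps are also condition-specific, yet Baseline has all study apps set up before randomization. In this protocol, being specific to a condition does not reliably date a step. Study Removal itself labels joining as on-boarding, and the list in Exclusion Criteria is open-ended. This stands in part: joining after allocation is the likelier reading, but it is not stated. The app wording needs clarifying too.

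**Silence is not a bar.** Being removed from the study does not mean going unassessed here, because two of the four grounds carry that label and still have follow-up. The Follow-ups section addresses participants without exception. This stands: follow-up under grounds 1 and 3 is unstated, not forbidden, so missing data are possible and not certain.

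**Analysis is already covered.** A reader might infer that removed participants leave the analysis or the denominators. The documents do not say so. Intent to treat and the planning number of 35 point to everyone randomized being counted. The plan also has missing-data sensitivity analyses, and multiple imputation above 5% missing.

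**Little is lost.** The weight model uses all weekly scale weights, so someone removed late for inappropriate content would already have contributed data. The loss is nearly complete only for a non-joiner removed at the start. Someone who never enters the program may also be a genuine feasibility loss. Both points stand, and the second is a reason to report non-joining separately.

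**Conclusion.** The inconsistency is real and worth correcting, but its likely effect is modest. Study Removal lists a step that appears to follow allocation among those whose non-completion means removal from the study. It states no 6-month assessment for people removed that way or for inappropriate content. Applied literally, this could create avoidable missing outcomes and non-retention, which sits badly with intent to treat.

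The size is 2.9 points of an arm's retention per removed person who would have completed, against a planned half-width of 11.8 points. This rests on arms of 35, a fixed denominator, and no assessment after removal. The number affected is unknown. It is probably small, because eligibility requires recent Facebook activity, those unwilling to use Facebook for the study are excluded, and all set-up steps come first.

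A reader might infer that one such removal would turn a feasibility success into a failure, since it can move an arm from above to below 85% and 73.2%. The documents do not support that. The 85% is an assumed observed value used to illustrate precision, not a pass mark, and no conclusion is shown to change.

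**What to change.** - **Reconcile the sections.** Align Study Removal with Study Design, Exclusion Criteria, Baseline and the Facebook Group section so that on-boarding failure means study exclusion only for steps completed before randomization. Clarify which apps are set up before allocation.
- **State the denominators.** Every randomized participant stays in the retention and app-use denominators and in the CONSORT diagram. Report non-joiners separately for engagement, so that their zeros are neither hidden nor mixed in.
- **State the follow-up.** Every randomized participant, including those removed under grounds 1 and 3, is invited to the 6-month weigh-in and survey unless they decline contact. Where a shared focus-group call is unsuitable, as it may be after removal for harassment, use the e-mailed questions in Focus groups or the one-on-one interview in Potential risks.
- **Say which items apply.** Group climate and program feedback questions may mean little for someone who was never in the group.

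Decisions on removal from the intervention stay with the study team.

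**Cost.** A wording edit, a few extra invitations, and the $100 in Payment to Participants for each additional completed follow-up. With 1, 2 or 3 people per arm in two arms, all completing, that is $200, $400 or $600. Feasibility figures with explicit denominators may look slightly less favourable.
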